### **Safety Measures During Physical Activity**

Exercise interventions are conducted on-site and all sessions are conducted and supervised by **trained PBRC exercise interventionists**, who monitor potential adverse experiences and symptoms. During the physical activity sessions a defibrillator and on-site trained staff are available to deal with medical emergencies. Also, institutional and community EMS services are activated if needed. Participants will be taught the importance and proper method of **warming-up** prior to and **cooling-down** following structured activity sessions. Heart rate will be monitored throughout the intervention sessions. If at any point during a physical activity session, participants develop chest pain, shortness of breath, or dizziness, they are instructed to rest and to contact their physicians if these symptoms persist or recur with further physical activity.

Procedures to minimize discomfort include **warm-up and cool-down activities** that include stretching, light walking or cycling. Participants are also **supervised and instructed** on correct physical activity techniques.

If for any reason the participant reports an injury, chest pain, shortness of breath, or dizziness, they are referred to their doctor, or the study clinician calls the doctor or other health care provider. In addition, specific criteria for **suspending or stopping physical activity** are developed to adjust the program for **intercurrent illness**.

### **Stopping Rules**

There is more than minimal risk for participating in this trial. Nevertheless, in addition to monitoring recruitment and compliance to the intervention, we also will monitor the rates of injury in our participants. The safety officers, in conjunction with the study investigators, will alert the IRB and DSMB if a larger than reasonably expected injury rate occurs in the treatment groups. Other issues that are related to the stopping rules include:

- New information – It is unlikely that new information will become available during this study that would result in discontinuing the trial.
- Limits of assumption – It is possible that the value of data analysis will be limited by differences between the intervention groups at baseline or because of study dropouts or missing data. Baseline differences will be analyzed annually and effects on the power to detect differences in the outcome measures will be evaluated and discussed with the PI, safety officer, and the USARIEM Project Officer. Although an excessive number

of dropouts could occur, this has not been our past experience. In similar studies completed by USARIEM, the dropout rate was approximately 10%. If the dropout rate for the proposed study exceeds 20%, the safety officer will initiate a meeting with the PI to discuss strategies to increase retention. If the dropout rate exceeds 50%, the safety officer will meet with the study investigators to determine whether or not the study should continue.

- Limit of rules – We acknowledge that circumstances, other than what are listed, may justify stopping the study.

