## Randomization

Immediately following phase 1 testing on day 14, participants will be randomized to one of two experimental groups, either a 28-d (live-in), 55% energy deficit phase (DEF) or a 28-d (live-in), 55% energy deficit phase with exogenous testosterone administration (DEF+TEST). A randomization scheme will be determined using a block design (n=60) and age stratification (< 29 years or ≥ 29 years). Randomization will be done by a biostatistician with no direct study affiliation. Prior to the start of the study, the randomization schedule will be given to the pharmacist. The PBRC clinical research pharmacist will have no direct contact with participants. Treatment administration will be performed by a physician assistant, nurse practitioner, or nurse who will not be aware of treatment assignments. Participants and all study personnel will be blinded to treatment group. The code will be kept as a locked electronic file on a secure server by the pharmacist until study completion or there is a need to break the code for safety of the participant.

## Phase 2: 55% Energy Deficit (live-in diet & activity control). Day 15–Day 42

- During the energy deficit phase, participants will live on Pennington Biomedical's inpatient unit in a 24-hour-a-day controlled setting. Once a day, participants will have their vitals (BP, pulse) measured. All meals will be eaten on the unit and monitored. Daily, participants will be weighed. Additionally, a wrist-worn accelerometer will be used throughout phase 2.
- Throughout phase 2, participants will complete supervised exercise sessions 1-4 times per day. Every 2 weeks, participants will undergo submax met carts for each mode of exercise utilized.
- Participants will consume 100 mL/d  $^2\text{H}_2\text{O}$  (i.e., heavy water) from day 15 to 42.
- Participants will be asked to provide a saliva sample on days 15, 19, 23, 27, 31, 35, and 39 to assess body water enrichment.
- Blood draws will occur on days 28 and 42.
- Cognitive testing will be performed on days 15, 20, 22, 27, 29, 34, 36, 40 and 41 over a 1.5-2 hour period each day.
- A DXA scan will be done on days 28 and 39.
- A 1 hour fMRI will be done on days 36, 37, and 38.
- An injection (placebo or testosterone) will be administered on days 15, 21, 28, and 35.
- Eating Inventories (TFEQ, FCI, FCI trait) will be completed on day 42.

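### The yearly by-arm baseline review in Stopping Rules needs the allocation mid-trial, while Randomization keeps the code locked and nothing reconciles the two

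*Combined protocol and SAP*

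**What the plan says.** Under Stopping Rules, a list is introduced by "Other issues that are related to the stopping rules include". Its item on limits of assumption warns that the value of the analysis may be reduced by "differences between the intervention groups at baseline or because of study dropouts or missing data". It then sets a task: "Baseline differences will be analyzed annually and effects on the power to detect differences in the outcome measures will be evaluated and discussed". The people named for that discussion follow: "discussed with the PI, safety officer, and the USARIEM Project Officer". The DSMB is not among them, although the same section names it as a recipient of injury-rate alerts.

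Under Randomization, the blind is stated broadly: "Participants and all study personnel will be blinded to treatment group". Custody of the allocation is equally plain: "The code will be kept as a locked electronic file on a secure server by the pharmacist until study completion". The only other ground for opening the code is a participant's safety. The same section has the randomisation done by a biostatistician who is not affiliated with the study.

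Three other sections bear on the point. Data and Safety Monitoring Board plans a four-member board that includes a biostatistician. Roles and Responsibilities gives the PI the leading role in data analysis. Primary Study Endpoint has the PI and the medical investigator decide whether a participant continues when a procedure is refused or cannot be done.

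**The concern.** Baseline differences between arms can be computed only by someone who knows which participants belong together. The Stopping Rules task therefore uses the allocation during the trial for a purpose that is not safety, and the Randomization section allows no such use. Staff cannot follow both sections as written.

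The recipients raise the stakes. The PI leads the analysis and shares decisions about whether participants continue, so by-arm information in that person's hands is what the blind exists to prevent. The safety officer and the USARIEM Project Officer are also outside the DSMB, the body that would normally hold such information. The stated purpose, a check on power, does not need allocation at all, so the risk buys little.

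**Working it through.** **1. The two sections side by side.**

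| Question | Stopping Rules | Randomization |
|---|---|---|
| What is compared or held? | Baseline data between the intervention groups | The allocation code, in a locked file |
| When? | Annually | Until study completion or a participant-safety need |
| Who is involved? | PI, safety officer, USARIEM Project Officer | Pharmacist holds the code; all study personnel blinded |
| Masked labels or independent analyst for this task? | Not stated | Not stated |

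An annual review of power is neither study completion nor a participant-safety need, so neither exception covers it.

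**2. Timing.** Experimental Design and Overview expects enrolment from spring 2016 to about summer 2017 and all data by September 2017. An annual review would fall while the trial is blinded, probably once.

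**3. The plan's own sample size.** Inputs from Table 2: difference 3.0 − 2.25 = 0.75 kg, SD 0.75 kg, alpha 0.05, power 0.90. Objective I: Statistics makes the tests two-sided.

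n per group = 2 × (1.960 + 1.2816)² × (0.75/0.75)² = 21.01, rounded up to 22. The exact t-test gives 22.02 (power 0.8997 at 22). The stated 22 per group reproduces.

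**4. What baseline imbalance does to power.** Normal approximation: power = Φ[0.75 / (0.75 × √(2/n)) − 1.960].

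- At n = 25 per group, √(2/25) = 0.2828, so power = Φ(3.536 − 1.960) = Φ(1.576) = 94.2%.
- A chance standardised difference in one baseline variable has a 95% range of ±1.96 × 0.2828 = ±0.55 SD at this size.
- Adjusting for a covariate that is out of balance by d SD multiplies the variance of the treatment contrast by 1 + d²/4:

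| d (SD) | 1 + d²/4 | Power at 25 per group |
|---|---|---|
| 0 | 1.0000 | 94.2% |
| 0.25 | 1.0156 | 93.9% |
| 0.50 | 1.0625 | 92.9% |
| 0.75 | 1.1406 | 91.2% |

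Even 0.75 SD, which lies outside the chance range above, leaves power over the planned 90%.

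**5. What loss of participants does to power.** Same formula with no imbalance:

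- 20 per group: Φ(3.162 − 1.960) = 88.5%.
- 15 per group: Φ(2.739 − 1.960) = 78.2%.

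Moving from 25 to 20 per group costs 94.2 − 88.5 = 5.7 points, against 94.2 − 92.9 = 1.3 points for an imbalance of 0.5 SD. Overall dropout can be counted without the code.

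**6. Whether SD can be watched blind.** With 1:1 allocation, the SD of all participants taken together is √(SD² + difference²/4). On Table 2's inputs this is √(0.5625 + 0.1406) = 0.84 kg if the hypothesised effect is present, and 0.75 kg if there is none. A blinded pooled SD can be judged against that range.

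**The case against.** The strongest reply is that a comparison needs group membership, not group identity. With masked A/B labels, the unaffiliated biostatistician who produced the schedule could run the comparison and pass on only its implication for power. The text promises no by-arm table to anyone; what it sends to the three recipients is a discussion of effects on power. All of this is fair. A reader might infer from the two sections that the code will be broken, or that the PI will be unblinded. The documents do not support that: they are silent on who does the work and under what labels. That silence is also the defect. Nobody is assigned, no masking is required, and membership must still be obtained from an allocation list whose permitted uses do not include this one.

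A second reply is that the harm is limited. Baseline measures precede randomisation on day 14 and the first injection on day 15, so they carry no treatment effect, reveal nothing about efficacy and spend no alpha. Probably only one such review would occur. This stands, and it limits the seriousness. It does not make the two sections compatible.

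**Conclusion.** The conflict is real and unresolved. One section calls for a by-arm analysis during the trial; the other closes the code to it. The blind is at risk from a step that tells the team little about power: about 1.3 points for an adjusted 0.5 SD imbalance at 25 per group.

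Three stronger readings should be avoided.

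- A reader might infer from the heading that baseline imbalance is treated as a reason to stop. It is not. No criterion or action is attached to imbalance, and the only continue-or-stop step in that item concerns attrition: "If the dropout rate exceeds 50%, the safety officer will meet with the study investigators to determine whether or not the study should continue".
- A reader might calculate how often a sound randomisation would produce a nominally significant baseline difference. The plan names no test, threshold or list of variables for this review, so such a figure would have no consequence in it.
- A reader might conclude that imbalance says nothing about power. It says a little, as the working shows.

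The power figures assume Table 2's difference and SD, the normal approximation, one covariate and an adjusted comparison. Residual SD is held at 0.75 kg, so no credit is taken for a prognostic covariate. The mixed model in Objective I: Statistics lists no baseline covariate, so the adjustment is this check's assumption. The finding of a conflict depends on none of these figures. The change should be made, but as a correction of wording and not as evidence that the trial is compromised.

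**What to change.** In Stopping Rules, replace the annual by-arm baseline analysis discussed with the PI, safety officer and USARIEM Project Officer. In its place, specify a blinded annual review of three quantities computed without allocation, as the check on power: the pooled SD of lean-mass change, the overall dropout rate and the amount of missing data.

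If a by-arm baseline table is still wanted, add one sentence. The unaffiliated biostatistician prepares it under masked labels, and it goes only to the DSMB biostatistician in closed session. Add this limited use to the Randomization section so that the two sections agree.

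The cost is a protocol wording change with no new visits, procedures or participants, and the DSMB already has a biostatistician. The PI and the USARIEM Project Officer lose one interim by-arm summary.

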### **Withdrawal of Subjects**

We will attempt to retain program participants once randomized at a retention rate of 80% for study completion through Day 42 and close-out visit. It is our desire to analyze results on all participants who were included into the program (e.g. completed SV1 visit). In accordance with the declaration of Helsinki/Tokyo/Venice/Hong Kong, participants have the right to withdraw from the program at any time for any reason. The investigator also has the right to withdraw participants from the program treatments in the event of inter-current illness, adverse experience, treatment failure, protocol violation, or other reasons. Should a participant decide to withdraw from treatment, all efforts will be made to complete and report follow-up observations as thoroughly as possible.

### **Risks to Subjects**

This study does not involve major risk to screeners and trial participants. Efforts to minimize the potential risks of the assessment methods and outcome variables include frequent monitoring by the investigators to assure that no participant suffers any adverse effects from participating in the research. The study procedures include:

- $^2\text{H}_2\text{O}$  (i.e., heavy water). The extra neutron in the heavy water is not radioactive and has no risk. Children and pregnant women have been given this "special" water.
- Body weight. There is no risk to participants who record their body weight.
- Blood Pressure Testing. Participants may experience temporary discomfort during blood pressure recordings due to the pressure of the cuff on their arm.
- Venipuncture (blood draw). There is the possibility of pain and bruising at the vein on the participant's arm where the needle is inserted. Aseptic (sterile) technique and trained personnel minimize these risks.
- Venous catheterization. There is a possibility of pain, bruising, or infection at the site of the needle insertion for the IV line. Trained personnel minimize this risk.
- Dual Energy X-ray Absorptiometry (DXA). The amount of radiation used for this procedure is very small. The radiation dose for this scan is equivalent to the radiation an individual is naturally exposed to in the environment in less than one day. The completion of 6 scans over the course of the trial is 500 times below the limit for radiation exposure per year. Per Pennington SOP, the quantity of scans completed in the trial is within the 10 DXA scans per year limit.

- Functional magnetic resonance imaging (fMRI). There are no known biological risks associated with magnetic resonance scanning. It has been used routinely for over 20 years. It produces side effects in very few situations. Those situations include:
  - **Metal**: Because the magnetic resonance machine uses a magnetic field, it can move any metallic objects that are inside the body. *This disruption of metal inside the body is extremely dangerous and may even be life threatening*. If the participant thinks he/she may have a cardiac stent, metallic implant, metallic piercings, shrapnel, or any other metallic material in the body, it is of utmost importance that the participant alert the study coordinator or MR technician. If the participant has metallic materials in the body that cannot be removed, we will exclude the participant from this study.
  - **Electronics**: Magnetic resonance imaging involves the use of radio frequency energy that can disrupt the functioning of electronic devices. If the participant possesses a pacemaker or any other electronic medical device inside the body, the participant will be excluded.
  - **Tattoos and cosmetics**: Some tattoos and cosmetics contain metallic materials that can heat up during scanning, especially if they are located on the part of the body being scanned. If the metallic material heats up enough, the participant may feel an uncomfortable burning sensation, and a skin burn may develop. In some cases, the amount of metallic material in the area being scanned is so excessive that the scan cannot proceed without risk of a burn developing. In other cases, a cold compress placed over the metallic material can be used to prevent burning.
  - **Confinement**: During the MR scan, the participant will be lying down on a table inside of a metal tube. The metal tube is a confined place. This might produce a feeling of claustrophobia, which can be distressing. A participant who has experienced claustrophobia in the past might become too distressed to complete the scan. In this case, the scan will be halted.
  - **Noise**: The MRI machine creates a loud, rhythmic noise that sounds like grinding or churning. This can be distressing to those who are sensitive to loud noises. The participant will be provided with earplugs to reduce the noise. But, if the participant finds the machine noises distressing, the MR technician can halt the scan.
  - **Peripheral nerve stimulation**: During the MR scan, the magnetic field around the body goes through rapid changes. These changes are all within safety limits set by the Food and Drug Administration. But, some people experience twitching in the nerves of their arms or legs as a result of these magnetic field changes. This twitching is generally not painful, and it stops at the end of the MR scan. But the feeling of inadvertent muscle twitching may make individuals feel disoriented or uncomfortable. Any participant who experiences this and wishes to stop the scan as a result will be allowed to do so.
  - **Electrical stimulus**: The BioPac device providing painful electrical stimulus has been safely applied in human subjects under a variety of conditions. Although the experimental design requires that the stimulus be painful, the electrical stimulation has no physical effects that last

beyond the duration of the task. There is a risk that the application of a painful stimulus may be psychologically distressing to the participant. In this event, the task will be terminated.

- **Mental tasks performed during fMRI:** There are no anticipated risks from performing these tasks.
- **Self-report Questionnaires.** There are no anticipated risks from completing self-report questionnaires. If signs of minor stress or fatigue are apparent, participants will be given time to take a break from completing the questionnaires. It is estimated that the questionnaires will take from 90 to 120 minutes to complete. The questions contained in some of the questionnaires may make people feel uncomfortable since they ask about topics such as how they feel about their body size. Responses to the questions will be coded to protect confidentiality, and participants may choose to not answer questions.
- **Accelerometry.** There is no risk associated with measuring activity with accelerometers. Accelerometers fit comfortably on the participant's arm and at the waist and can easily be removed should they become uncomfortable.
- **Archive of Biological (Blood) Sample.** The primary risk to participants regarding blood to be banked for future research is the risk of loss of confidentiality and/or privacy. Most banks need to maintain a link between the identities of donors and coded specimens to be able to collect valuable clinical follow-up information about the donor. To insure participants' privacy and confidentiality, their samples will be labeled with a unique series of letters and numbers. Pennington Biomedical will store these samples with unique identifiers and a minimum number of personal identifiers to meet laboratory standards. Storage and disposal of tissue will be conducted in a manner conforming to the appropriate care and handling of biological specimens as outlined through the Institutional Biohazard Committee Guidelines.
- **Muscle Biopsy.** Mild to severe pain, soreness, bruising, and a small scar are common risks. A hematoma (collection of blood in the tissue)) may occur. There is a slight risk that a superficial nerve may be cut; the nerve may heal, or it may result in a permanent loss of sensation in the skin at the biopsy site. Although infrequent, there is risk of infection at the biopsy site, which may need treatment with antibiotics.
- **Metabolic Chamber.** A participant may experience some level of claustrophobia or discomfort from staying in the chamber and being continuously monitored by a camera. However, participants will not be locked in and will be able to open the door in case of an emergency. The camera has been installed for participants' safety and no one is allowed access to the monitor except chamber personnel.
- **24 Hour Urine Collection.** There are no known risks of collecting urine into a container.
- **Fecal Collection.** There are no known risks of collecting a fecal sample.
- **Consumption of D3-creatine (D3Cr) (60 mg capsule).** This is a stable isotope, and thus is not radioactive. Consuming this isotope at levels described in this study is considered safe.
- **Testosterone.** Potential side effects of testosterone treatment include acne, oiliness of skin, increased growth of body hair, breast tenderness, a reversible increase in hemoglobin, sleep apnea, leg edema and weight gain.
- **EKG.** There are minimal risks associated with this test. There is a small possibility there may be some redness or irritation while cleaning the skin prior to applying the

electrodes or if a participant happens to be allergic to the adhesive on the electrodes.

- Exercise testing. There is minimal risk of injury or a cardiovascular event during exercise testing. We believe the risk of an event during exercise testing is minimized with a pretest review of the medical history, physical examination by a physician or mid-level health care professional, use of a highly trained staff, and well-defined emergency procedures. Participants may experience temporary discomfort during blood pressure recordings due to the pressure of the blood pressure cuff on the arm. All tests are conducted in the presence of an exercise physiologist with extensive experience in conducting maximal exercise tests as well as a Research Associate specializing in cardiology. All laboratory staff are trained in basic CPR and/or ACLS (advanced cardiac life support). In the event of a life threatening emergency, the subject would be treated with ACLS by a staff M.D. and research nurses and subsequently be transported to the nearest acute care medical-surgical facility via Emergency Medical Services which is a parish wide paramedic response unit. The closest facility is approximately 0.25 miles away.
- Exercise interventions. The proposed exercise interventions are unlikely to cause major problems. We have conducted numerous exercise training studies and have never had a serious adverse event. There is the possibility of adverse events ranging from minor musculoskeletal problems to, in very rare cases, cardiovascular events. Exercise bouts will include a variety of modes (walking, cycling, elliptical, running, and pack walking) and intensities (low to high) at the discretion of the trainer to ensure compliance to the intervention as well as minimizing injury. Occasionally study participants experience minor orthopedic problems, but most are self-correcting with rest and standard first aid. These orthopedic injuries will be minimized by gradually progressing participants to their prescribed dose at the start of the study and alternating exercise sessions between cycle ergometers and treadmills as necessary. Exercise supervisors are trained in first aid and basic CPR. Each staff member is trained in either advanced or basic life support, and an automated external defibrillator and fully-stocked crash cart are kept on site. Although some study participants will be at moderately elevated risk for CVD, they will receive a thorough health screen including a physical examination by a study physician or mid-level health care professional and a maximal exercise test. According to the available data on adverse events resulting from the types of exercise proposed here, risk should be low in this study. Fatal events during exercise are extremely rare.
- Energy Deficit. There is a small risk of hypoglycemia when starting a diet lower in calories than participants are accustomed to and increasing caloric expenditure via exercise. Regular blood work and monitoring (including vitals) will be completed throughout the phases for safety checks. Prior to inclusion in the trial, all participants are screened to exclude those with medical or mental disorders that are unsuitable for the trial. Additionally, a barriers interview will be completed during screening to further explain study demands, assess barriers to participation, and screen for psychological and behavioral contraindications to the trial. The clinical site physician will review the medical procedures and psychological health of each participant and attest to suitability for inclusion to into the trial. Once enrolled in the trial, study staff with psychological and behavioral expertise will make daily rounds on the unit to assess mental stability and health of the participants. Any participant

displaying undue distress or other negative psychological symptoms as a result of the trial procedures, the PI and MI will assess if continuation in the trial is warranted. An on-call physician is also available after hours and on weekends.

